While dietary components support the creation of new neurons, cognitive training promotes integration of neurons into neural networks.(19-21) Speed of processing training, in particular, results in very large performance gains(22-24) that are maintained for years.(25, 26) "Speed training" targets fluid mental processing speed and reduces the length of time needed to process more and more complex information.(27) In a secondary analysis of data from the largest cognitive training trial ever conducted, we showed speed training had a large effect among participants with fewer than 12 years of education; the effect size was 50% larger in those with fewer than 12 years of education compared to the subsample with 16 or more years.(28) The training advantage in the less educated carried out to 5 years.

At this time, there are no published randomized trials of speed of processing training combined with MIND foods. Nor are there published randomized trials of MIND foods or speed training properly designed and powered to assess effects in older adults with low education. Using a 2x2 factorial design, we propose to test in a randomized controlled trial the effects of speed training and MIND foods in older adults with low education. The ultimate goal of this line of research is to prevent or delay AD in this vulnerable group.

This study will enroll older adults receiving care in Eskenazi Health who have 12 years of education or less. Interested and eligible individuals who consent to the study will receive a study-provided tablet running our professionally designed MINDSpeed app. The app will provide each participant with 12wks of access, support, and incentives for all 4 study arms: 1) MIND food + Speed training, 2) MIND food + Speed training control, 3) MIND food control + Speed training, or 4) MIND food control + Speed training control. We refer to the combinatorial MIND food and Speed training intervention as MINDSpeed, while the combination of food control and speed training control we refer to as Double Control.

The primary specific aim of this pilot clinical trial is to determine MINDSpeed effects on an executive cognitive composite (ECC) score relative to Double Control. The primary hypotheses are that MINDSpeed is more effective than MIND food or Speed training alone and all are more effective than Double Control in improving the objective ECC measure at immediate post-training and 6-month follow-up.

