VBM grey matter density (GMD) images, DTI FA and MD images, task-related contrast images, RS-fcMRI component maps, and ASL CBF images will be compared between those receiving the combined intervention, a single intervention, and control cross-sectionally and longitudinally on voxel-wise and ROI levels. Cross-sectional voxel-wise analyses will compare the scans between groups at BL, PT, and FU. Longitudinal voxel-wise analysis will model time-by-group interactions using a two-way Analysis of Covariance (ANCOVA) model. All voxel-wise analyses will be performed in SPM8 (or SPM12). For regional analysis, we will extract a mean value for ROIs from the final stage preprocessed scans. Specifically, cross-sectional and longitudinal change in regional brain atrophy (i.e., MTL, frontal lobe), WM integrity (i.e., FA, MD from MTL WM tracts), task-related fMRI activation (i.e., activation from task-specific regions), resting-state connectivity (e.g., DMN connectivity from medial parietal lobe and MTL, etc.), and cerebral perfusion (i.e., whole brain, frontal lobe, etc.) will be compared between groups using values extracted from hypothesized target ROIs (see Analytic Plan).

Cost. We will track all personnel, equipment, technology, and support costs associated with delivering the interventions thus allowing an estimation of intervention costs on a per subject basis.

Power and Sample Size. The primary analysis of the study focuses on the evaluation of the effectiveness of the interventions on the cognitive outcome, ECC. We therefore determined the sample size to ensure adequate power for this analysis. In these prior studies, speed of processing training was found to have an effect size (ES) of 1.4 standard deviation (SD) at immediate post-training (PT) and 1.2 SD at one year PT on processing speed outcomes.(22) MIND diet is a brain health optimized hybrid of the Mediterranean-DASH diets, and the latter were found to have an effect size of 0.44 to 0.56 SD on executive function and speed of processing(136). There are no published trials of speed of processing training combined with MIND diet but we expect a large effect size of the combined intervention. With an overall alpha level of 0.05 for six Bonferroni-

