adjusted two-sided comparisons, a conservative estimate of the correlation of 0.7 between baseline and followup based on prior studies, and 15% attrition rate (in our recent GRACE trial of 951 older adults—62% had < 12yrs of education—91% completed the 6-month follow-up assessment)(73), the sample size of up to 50 participants per treatment arm will yield 80% power to detect an effect size of >0.5 SD based on the constrained longitudinal data analysis (cLDA).(137) The cLDA (138) has been shown to produce greater efficiency and handle missing data more flexibly with valid inference when data are missing at random.(137, 139). Cognitive aging studies support an effect size of over one-half standard deviation as clinically meaningful.(140-142)

Exploratory Aims and Power: Outcomes include inflammation, metabolic function, oxidative stress, and hippocampal structure and function (via MRI). For non-imaging outcomes, we will have a full sample and adequate power to detect effect sizes of 0.6. Imaging creates anxiety and discomfort for some, however. Thus, in addition to using information and communication strategies shown to reduce imaging anxiety(143) we will complete imaging on the minimum necessary. From the literature, we anticipate large effect sizes on the brain outcomes of hippocampal structure and function. Cognitive training has resulted in changes in brain structure with approximate effect size of 0.56 in left hippocampus volume following spatial navigation training among healthy younger and older men(144) and an approximate effect size of 0.47 in gray matter density (GMD) after the completion of a multidomain computerized cognitive training among healthy older adults.(20) In addition, our preliminary results showed an effect size of 0.5 in annual percent change in hippocampal volume and 0.8 in annual percent change in hippocampal GMD among older adults without MCI who are frequently engaged in reading and puzzle-solving compared to those who are not. Food interventions alone have had an effect size of 0.7 on hippocampal volume.(9, 56) Other studies support effect sizes of 0.64 to above 1.00 on functional connectivity.(145, 146) A one-half subsample of each arm (n=22 per arm) with an alpha level of 0.05 and a correlation of 0.7 between baseline and post-training provides 80% power to detect an effect size of 0.7 or larger for the brain imaging outcome.

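### Holm's step-down test would never reject less than the planned six-way Bonferroni at the same familywise 0.05, and the stated 80% power is for a single contrast

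*Combined protocol and SAP*

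**What the plan says.** Power and Sample Size fixes the error rate in one clause: "With an overall alpha level of 0.05 for six Bonferroni", continuing "adjusted two-sided comparisons". The other inputs are "a conservative estimate of the correlation of 0.7 between baseline and followup" and a "15% attrition rate". The result is that "the sample size of up to 50 participants per treatment arm will yield 80% power to detect an effect size of >0.5 SD" under the constrained longitudinal model. The six comparisons are not listed. They could be the six pairs of four arms, or three active arms against Double Control at two visits.

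The primary analysis paragraph of the Analytic Plan estimates arm contrasts at post-training and follow-up from the model and names no multiplicity procedure.

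In Specific Aims, the primary aim is one contrast: "to determine MINDSpeed effects on an executive cognitive composite (ECC) score relative to Double Control". The primary hypotheses go further. MINDSpeed is to be more "effective than MIND food or Speed training alone and all are more effective than Double Control", and this "in improving the objective ECC measure at immediate post-training and 6-month follow-up". That makes five directional contrasts (MINDSpeed against each component, and each of the three active arms against Double Control) at two visits.

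**The concern.** Single-step Bonferroni holds every comparison to 0.05/6, even after others have clearly been rejected. Holm's procedure relaxes the threshold as rejections accumulate, at no cost in familywise error. The contrasts most likely to benefit are the smaller ones. These include MINDSpeed against Speed alone, which shows whether food adds anything to training.

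The power statement is also easy to misread. It gives 80% for one comparison, while the hypotheses make five claims together, and no figure is given for the five. A reader planning the later-stage trial could take 80% as the chance of confirming the whole set.

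**Working it through.** **Inputs from the documents.** Familywise alpha 0.05 over six two-sided comparisons; correlation 0.7; up to 50 per arm; 15% attrition; effect 0.5 SD (all from Power and Sample Size). The five contrasts and two visits come from Specific Aims.

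**Reproducing the stated 80%.** Per-comparison alpha = 0.05/6 = 0.00833, so z = 2.638. Residual variance given baseline = 1 − 0.7² = 0.51 (SD 0.714).
- 50 analysed per arm: SE = √(2 × 0.51/50) = 0.143; 0.5/0.143 = 3.50; power = Φ(3.50 − 2.638) = 80.6% (79.7% with the t distribution).
- 50 × 0.85 = 42.5 analysed: SE = 0.155; 0.5/0.155 = 3.23; power = Φ(3.23 − 2.638) = 72.2% (71.0% with t). The effect with 80% power is (2.638 + 0.842) × 0.155 = 0.54 SD, which still fits the plan's wording of more than 0.5 SD.

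So the 80% is power for one contrast.

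**Why Holm never rejects less.** Order the p-values and compare them in turn with 0.05/6, 0.05/5, 0.05/4, 0.05/3, 0.05/2 and 0.05, stopping at the first failure. Every threshold is at least 0.05/6, so anything Bonferroni rejects, Holm rejects. Strong familywise control needs no assumption about dependence. In simulation no run contradicted this, and Holm's familywise error was at most 0.042. This holds whichever six comparisons are meant.

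**Size of the gain.** At least 200,000 simulated trials per setting: four adjusted arm means, six pairwise two-sided tests, pooled t, one visit. Patterns are in the order Double Control / food / Speed / MINDSpeed. They are assumptions, since the documents do not quantify the combined effect.

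| Pattern (SD) | Contrast | Analysed per arm | Bonferroni | Holm |
|---|---|---|---|---|
| 0/0.5/0.5/1.0 | each 0.5 SD contrast | 50 | 80% | 88% |
| same | same | 42.5 | 71% | 80% |
| same | MINDSpeed v Double Control | either | ~100% | ~100% |
| 0/0.5/1.4/1.9 | MINDSpeed v Speed | 50 | 80% | 93% |
| 0/0.44/1.4/1.84 | MINDSpeed v Speed | 50 | 66% | 85% |
| same | same | 42.5 | 57% | 78% |

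The 0.44 and 0.5 SD food effects lie in the plan's cited diet range of 0.44 to 0.56 SD. The 1.4 SD is its cited post-training effect of speed training. With those, MINDSpeed v Speed gains about 13 to 21 points. If only MINDSpeed works (0/0/0/0.5), or all effects are halved (0/0.25/0.25/0.5), the gain on the contrasts with a real effect is about 0.5 to 3 points.

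If the six are instead three arms against Double Control at two visits (post-training to follow-up correlation assumed 0.7), each 0.5 SD contrast in the first pattern goes from 80% to 91% at 50 per arm and from 71% to 85% at 42.5.

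**All five contrasts together**, pattern 0/0.5/0.5/1.0, each in the hypothesised direction:

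| Requirement | Analysed per arm | Bonferroni | Holm | Each at 0.05 |
|---|---|---|---|---|
| One visit | 50 | 45% | 66% | 79% |
| One visit | 42.5 | 30.2% | 51.5% | 67% |
| Both visits (correlation assumed 0.7) | 50 | 25% | 48% | not run |
| Both visits (correlation assumed 0.7) | 42.5 | 13% | 31% | not run |

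With 0/0.5/1.4/1.9 at one visit, joint power under Bonferroni is about 64% at 50 per arm and 51% at 42.5.

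**The case against.** Bonferroni is valid, simple, and comes with matching simultaneous intervals. It appears only in the sizing paragraph, where it is a conservative basis that does not bar a step-down test later. The trial is a pilot, and its primary aim is one contrast, MINDSpeed against Double Control, where Holm adds nothing if the effect is large. All of this stands, and it makes the point an efficiency gain rather than a correction.

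A reader might infer that, at the plan's own inputs, Bonferroni gives up 8 points on every contrast and leaves 45% power for the hypotheses as worded. The documents do not support that. The 0/0.5/0.5/1.0 pattern is not in them: they cite 1.4 SD for speed training (on processing-speed outcomes), leave the combination unquantified, and say only that the two components may be additive. The 8 points and 45% also leave out the stated attrition, and the 45% counts one visit where the hypotheses name two.

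Nor does low joint power argue for Holm by itself. If success means all five contrasts are significant, that single claim needs no adjustment. Testing each at 0.05 gives about 79%, against 66% with Holm. Holm's advantage matters when each contrast is a claim in its own right. Finally, if the six are three arms against Double Control at two visits, MINDSpeed against its components lies outside the family, and the five-contrast Bonferroni and Holm figures do not apply.

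**Conclusion.** A cheap improvement, not an error. That Holm never rejects less at the same familywise 0.05 is certain and does not depend on which six comparisons are meant. The size of the gain does depend on the truth: 8 to 9 points per 0.5 SD contrast under the assumed additive 0/0.5/0.5/1.0 pattern, about 13 to 21 points for MINDSpeed v Speed if speed training has its cited 1.4 SD and food 0.44 to 0.5 SD, and 3 points or fewer if only the combination works or effects are half as large.

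The stated 80% reproduces as power for one contrast with 50 analysed per arm. It is not power for the five-part hypothesis, which the plan does not give. The joint figures shown above depend on the assumed pattern, on all pairwise contrasts forming the family, and on how attrition and the two visits are counted.

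**What to change.** In the primary analysis paragraph of the Analytic Plan, list the six comparisons, including the visit or visits, and state that they are tested with Holm's procedure at overall two-sided 0.05. Shaffer's version may be used only if the six are all pairwise contrasts of the four arms at one visit. Report Bonferroni simultaneous intervals beside the Holm p-values.

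In Power and Sample Size, say that 80% is per contrast. For any joint figure, show the assumed effect pattern, the attrition and the visits required, and say whether success means all five contrasts or each on its own.

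The cost is a few sentences and no extra participants. The small downside is that the Bonferroni intervals may not always agree with the Holm decisions: a contrast can be significant by Holm while its interval includes zero. One sentence should say that the Holm decision governs. The change should be made before outcomes are compared by arm.

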The *primary analysis* of the intervention effect on ECC will be performed using the constrained longitudinal data analysis (cLDA) proposed by Liang and Zeger.(138) Repeatedly measured ECC outcome at BL, PT, and FU will be modeled as dependent variables with the baseline mean responses constrained to be the same across intervention arms due to randomization. This model is flexible in handling missing data and has been shown to provide greater power than other models when testing intervention effects and yields valid results when data are missing at random. The clustering effect of repeated measures within a subject will be accommodated using a random subject effect. Time of measurement (BL, PT, FU) and its interaction with intervention arm will be included in the model. The time of measurement is considered as a categorical variable to allow non-linear time effect. Intervention effects are captured by the significant interaction effect. Comparison of outcome measures across intervention arms at PT and FU will be estimated based on the

model using appropriate contrasts. In order to assess whether the intervention effect is affected by physical activity change, weight change, or other factor, we will examine change patterns across intervention arms. If the change pattern differs across intervention arms, that factor will be controlled by including its main effect and interaction with the intervention arm in the primary analysis for intervention effect on memory.

Exploratory Analyses. Feasibility hypotheses are 80% or greater intervention adherence and acceptability, and no serious adverse events. These will be estimated using the 95% confidence intervals. To compare safety, we will estimate the difference in rates of adverse events across the intervention arms using 95% confidence intervals. Hypotheses of improved self-reported outcomes including depression, cognition and engagement, quality of life, and IADL will be examined using the cLDA methods described immediately above.

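### With 15% attrition, 50 per arm gives about 72% power at 0.5 SD for a pairwise comparison at one visit, and reaches 80% at about 0.54 SD; the plan does not say which test its 80% refers to

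*Combined protocol and SAP*

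**What the plan says.** The inputs and the result stand together in Power and Sample Size. The error rate is given as "With an overall alpha level of 0.05 for six" Bonferroni-adjusted two-sided comparisons; six is the number of pairs among four arms (4 × 3 / 2). The other inputs are "a conservative estimate of the correlation of 0.7 between baseline and followup based on prior studies, and 15% attrition rate". An earlier trial is cited beside the attrition figure, in which "91% completed the 6-month follow-up assessment". The conclusion is that "the sample size of up to 50 participants per treatment arm will yield 80% power to detect an effect size of >0.5 SD", using constrained longitudinal data analysis (cLDA).

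The same section says "Cognitive aging studies support an effect size of over one-half standard deviation as clinically meaningful". For the diets on which MIND is built it says "the latter were found to have an effect size of 0.44 to 0.56 SD on executive function and speed of processing".

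Specific Aims hypothesises that MINDSpeed beats each component alone and that all three active arms beat Double Control, both immediately post-training (PT) and at 6 months (FU). The Analytic Plan relies on the arm-by-time interaction and adds that "Comparison of outcome measures across intervention arms at PT and FU will be estimated" by contrasts from the model. Within-person clustering "will be accommodated using a random subject effect".

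No formula, number of completers, powered visit or PT–FU correlation is given.

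**The concern.** Because attrition is listed as an input, a reader will take the 80% as power after attrition, for the comparisons that the plan describes. For one pair of arms at one visit, the other inputs alone already use up all 50 per arm and leave no room for a 15% loss.

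At stake is how a null result would be read. For effects in the plan's diet range, power after attrition runs from 58% to 84%. That bears on MIND food versus Double Control. If the two components add (my assumption), it also bears on MINDSpeed versus Speed training alone. A non-significant food comparison could be taken as coming from a test with 80% power when it had less. The same figure could also carry over into the later prevention trial mentioned under Study Considerations.

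**Working it through.** **Inputs (Power and Sample Size).** α = 0.05/6 = 0.00833 two-sided, so z = 2.638; z for 80% power = 0.842; baseline correlation ρ = 0.7; attrition 15%; 50 per arm.

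**Single-visit pairwise contrast under cLDA.** In SD units, SE = √(2(1 − ρ²)/n) with 1 − ρ² = 0.51, and power = Φ(δ/SE − 2.638).

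*The plan's figure without attrition.* n = 2 × 0.51 × (2.638 + 0.842)² / 0.5² = 2 × 0.51 × 12.11 / 0.25 = 49.4 analysed per arm. At n = 50, SE = 0.1428 and power = Φ(3.501 − 2.638) = 80.6%. The effect detectable with 80% power is 3.480 × 0.1428 = 0.497 SD.

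*With 15% attrition.* 49.4/0.85 = 58.1 enrolled would be needed. With 50 enrolled, 50 × 0.85 = 42.5 are analysed, SE = 0.1549, and power = Φ(3.227 − 2.638) = 72.2%. The detectable effect is 3.480 × 0.1549 = 0.539 SD.

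| Analysed per arm | Power at 0.5 SD | Effect at 80% power | Power at 0.44 to 0.56 SD |
|---|---|---|---|
| 50 (no loss) | 80.6% | 0.497 SD | 67% to 90% |
| 45.5 (91% completion) | 75.8% | 0.521 SD | 62% to 86% |
| 42.5 (15% loss) | 72.2% | 0.539 SD | 58% to 84% |

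A t-based calculation gives 79.7% at 50 and 71.1% at 42.5.

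**Timing of the loss.** A participant with baseline only adds nothing to a between-arm contrast, but one seen at PT and then lost adds some information about FU. From the information matrix of the four-arm, three-visit cLDA, at 0.5 SD:

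| 15% lost | PT power | FU power, PT–FU correlation 0.7 | FU power, PT–FU correlation 0.9 |
|---|---|---|---|
| all before PT | 72.2% | 72.2% | 72.2% |
| half before, half after | 76.7% | 73.0% | 75.1% |
| all after PT | 80.6% | 73.6% | 77.6% |

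FU stays below 80% in every pattern. The PT–FU correlation r is not stated; a single random subject effect makes all pairs of visits equally correlated, hence 0.7 as the base case.

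**Other tests that the 80% might refer to.**

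- *Joint 2-df arm-by-time test for a pair of arms, 0.5 SD at both visits.* Noncentrality = (n/2) × 2δ²/(1 + r − 2ρ²). The critical value is 9.575 and the noncentrality needed is 14.35. At r = 0.7, 2δ²/(1 + r − 2ρ²) = 0.5/0.72 = 0.694, so n = 2 × 14.35/0.694 = 41.3 analysed, or 48.6 enrolled. Power at 42.5 is 81.4%, falling to 77.9% at r = 0.75 and 74.5% at r = 0.8.
- *Mean of PT and FU.* The variance term is (1 + r)/2 − ρ². At r = 0.7 this is 0.36, which needs 34.9 analysed, or 41.0 enrolled. Power at 42.5 is 93.3%, 88.6%, 83.2% and 77.6% at r = 0.6, 0.7, 0.8 and 0.9.
- *Change score:* 58.1 analysed, 68.4 enrolled. *Follow-up score only:* 96.9 and 114.0.
- *One-sided 0.05/6, single visit:* 42.7 analysed, 50.3 enrolled. The plan states two-sided.

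**The case against.** The strongest objection is that attrition may well have been applied, to a different test. The Analytic Plan says that intervention effects are captured by the arm-by-time interaction. For two arms that is a joint test over PT and FU, and with all correlations at 0.7 it needs 48.6 enrolled per arm after 15% loss, close to 50. Two neighbouring figures point the same way. The imaging group is called half of each arm and given as 22; half of 50 is 25, while half of 42.5 is 21.25. The 8% margin of error for feasibility lies nearer the 7.5% from 170 participants than the 6.9% from 200 (at a proportion of 0.5), though it holds for both.

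This stands to the extent that a reader who infers that attrition was forgotten goes further than the documents allow. It does not rescue the 80% for the comparisons that the plan describes. The joint test needs equal effects at both visits, is below 80% by a PT–FU correlation of 0.75, and is not the visit-by-visit pairwise comparison in the hypotheses. The PT/FU mean also exceeds 80% at most correlations (up to about 0.86), but the plan does not name it.

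A second objection is that the plan writes greater than 0.5 SD and calls effects over one-half SD meaningful, and 0.54 satisfies both. That is right: the sentence is not literally false, and single-visit power after attrition is 82% at 0.55 SD. But the wording leaves the detectable effect undefined, and most readers will take 0.5 SD as the threshold.

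Third, this is a pilot, and the earlier trial kept 91%. At that rate single-visit power is still 75.8%.

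**Conclusion.** The concern holds for pairwise comparisons at a single visit. With the stated two-sided 0.05/6, correlation 0.7, 15% attrition and 50 randomised per arm, power at 0.5 SD is about 72% when the 15% have no outcome at that visit, and 80% is reached at about 0.54 SD. If all loss falls after PT, PT keeps 80.6% and FU has about 74% to 78% for a PT–FU correlation of 0.7 to 0.9. Confidence in this arithmetic is high. Confidence about how the 50 was derived is low, since no formula is shown.

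A reader might also infer that the trial is underpowered for its primary aim. The documents do not support that: they expect a large effect for the combined intervention, and at 0.8 SD (my assumption for large) power after attrition is 99%. The shortfall is about 8 points at 0.5 SD and matters mainly for the single-component and incremental comparisons. It also depends on the baseline correlation: at 42.5 per arm, power is 65.4%, 72.2% and 80.1% for correlations of 0.65, 0.70 and 0.75.

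**What to change.** Replace the power sentence with wording such as: *up to 50 randomised per arm with 15% attrition gives about 72% power at 0.5 SD, or 80% power at about 0.54 SD, for each pairwise comparison at a single visit (two-sided 0.05/6, correlation 0.7).* If the 80% was meant for a joint PT/FU interaction test or for a PT/FU mean, name that test and its assumed PT–FU correlation, and give the single-visit power beside it.

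This changes wording only, with no change to enrolment or analysis. The cost is a slightly less favourable stated power.
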